Poor and intermittent stream; Intermittent urination is usually a sign of significant underlying bladder problem, most often incomplete bladder emptying can predispose to urinary tract infections, bladder stone formation, and renal insufficiency (damage to the kidneys).

Incomplete bladder emptying; Incomplete bladder emptying occurs when the muscles of the bladder are not able to squeeze properly to empty the bladder.

Frequency; Its normal and how many times is too frequent to urinate.

Urgency; Urinary urgency occurs when the pressure in the bladder builds suddenly, and it becomes difficult to hold in the urine.

Nocturia; the need for patients to get up at night on a regular basis to urinate

Alpha Blockers: Alpha blockers are also known as α -blockers or α -adrenoreceptor antagonists, are a class of pharmacological agents that act as antagonists on α -adrenergic receptors.

Anticholinergic: Anticholinergic drugs block the action of a neurotransmitter called acetylcholine. This inhibits nerve impulses responsible for involuntary muscle movements and various bodily functions. These drugs can treat a variety of conditions, from overactive bladder to chronic obstructive pulmonary disorder.

USSQ: Ureteral Stent Symptoms Questionnaire; a psychometrically valid measure to evaluate symptoms and impact on quality of life of ureteral stents.

HYPOTHESIS:

Solifenacin group have better outcome in comparison to Tamsulosin.

MATERIAL AND METHODS:

Study Design: Comparative study

Setting: Study will be conducted Department of Urology, Liaquat National Hospital Karachi. It will include the patients who had have complaints voiding symptoms like increased urinary frequency, urgency dysuria, incomplete bladder emptying and supra pubic pain.

Study Duration: 6 months after approval of synopsis.

Sampling Technique: non-probability consecutive sampling.

Sample size: The sample size is calculated by using the mean \pm SD of USSQ score i.e. 76 \pm 8 in tamsulosin group and 61 \pm 8.8 in solefinacin group. Open Epi Software is used for sample size calculation by taking power of test = 90% and confidence interval 95%, the total calculated sample is 14 patients (7 in each group). To improve the power the study, we will have 30 patients in each group.

Sample selection:

Inclusion criteria:

- Between the ages of 20 and 50 years,

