Patient's data will be compiled and analyzed through statistical package for Social Sciences (SPSS) Version 25. Normality of the data will be checked by Shapiro wilk's test. Mean \pm SD will be calculated for quantitative variable for groups i.e. age, height, weight, body mass index, length of stent placed and total USSQ score. If the data is non normal, median (iqr) will be reported instead of mean \pm SD. Frequency and percentage will be computed for qualitative variables for groups like gender, any addiction, diabetes, hypertension, smoker, occupation, surgical procedure and indications of stent placement. ANOVA will be applied to see the mean differences between groups. Chi square test or Fischer exact test will be used for finding association between categorical variables. Post stratification will be done on age, gender, height, weight, body mass index, any addiction, diabetes, hypertension, smoker, occupation, surgical procedure and indications of stent placement to see the effect of these modifiers on outcome. P-value ≤ 0.05 will be considered as significant.

ETHICAL CONSIDERATION:

Conducting a randomized control trial (RCT) comparing alpha-blocker and anti-cholinergic drugs involves several ethical considerations. It's crucial to prioritize the well-being and rights of participants while ensuring scientific rigor. Here are some ethical concerns associated with this a trial:

1. Informed Consent:

Ensuring that participants fully understand the nature of the study, potential risks, benefits, and alternatives before providing informed consent. It will be clearly communicated that participation is voluntary, and individuals have the right to withdraw at any time without facing negative consequences.

2. Participant Selection and Equity:

Ensuring that the selection criteria for participants are fair and do not disproportionately exclude certain demographic groups, potentially leading to biased results.

3. Confidentiality and Privacy:

Safeguarding participant confidentiality and privacy by implementing robust data protection measures. Clearly communicating how participant data will be handled, stored, and shared to maintain trust and comply with relevant privacy regulations.

4. Publication and Reporting:

Committing to transparent and timely reporting of study results, whether positive or negative, to contribute to scientific knowledge and prevent publication bias.

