10. Mirani K K, Ather M H (August 08, 2022) Translation and Validation of the Ureteral Stent Symptoms Questionnaire in Urdu. *Cureus* 14(8): e27764. DOI 10.7759/cureus.27764

ANNEXURE-I PROFORMA

GROUP: _____

Serial No: _____

Case No: _____

Patient's Name: _____

Patient's contact #: _____

S/O, D/O, W/O: _____

Patient's Age: _____ years

Gender: Male Female

Height: _____

Weight: _____

BMI: _____

Any Addiction: Yes No _____

Diabetes: Yes No

Hypertension: Yes No

Smoker: Yes No

Occupation: _____

Surgical Procedure: _____

Indication of stent placement: _____

Date of stent placement: _____

Length of stent placed: _____ (cm)

Total USSQ score: _____

ANNEXURE-II USSQ(Stent in situ)

We are interested to know about various aspects of your health, following insertion of the stent and the effect the stent has had on your health.

**Please complete the following questionnaire, which has different sections.
Please answer all questions in each section.**

(We would be grateful if you could complete and post the questionnaire within seven days)

Please complete:

Today's Date: / /

Date of Birth: / /

You will see that some questions ask if you have a symptom occasionally, sometimes or most of the time.

Occasionally	=	less than one third of the time
Sometimes	=	between one and two thirds of the time
Most of the time	=	more than two thirds of the time

URINARY SYMPTOMS

Please answer the questions thinking about the urinary symptoms you have experienced following insertion of the stent.

Please put a tick in one box for each question

Please think about your experience since insertion of the stent.

U1. During the day, how often do you pass urine, on average?

Less than hourly	 5	Every 3 hourly	 2
Hourly	 4	Every 4 hours or more	 1
Every 2 hourly	 3		

U2. During the night, how many times do you have to get up to pass urine, on average?

None	 1	3	 4
1	 2	4 or more	 5
2	 3		

U3. Do you have to rush to the toilet to urinate?

Never	 1	Most of the time	 4

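### Age, height, weight and BMI are to be stratified as effect modifiers with no cut-points fixed, which loses information and leaves room for data-chosen cuts; a continuous group-by-variable term avoids both.

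*Combined protocol and SAP*

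**What the plan says.** In the combined protocol and SAP, the DATA ANALYSIS PROCEDURE section states that mean and SD "will be calculated for quantitative variable for groups i.e. age, height, weight, body mass index", among others. So the plan itself regards these four as quantitative.

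Later in the section it lists twelve factors for stratification. The sentence opens: "Post stratification will be done on age, gender, height, weight, body mass index". The rest of the list consists of factors that the plan treats as qualitative. The purpose is "to see the effect of these modifiers on outcome". The decision rule for all tests is "P-value ≤ 0.05 will be considered as significant".

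No cut-point, number of bands or rationale for banding appears in that section or elsewhere. The proforma in Annexure-I collects exact values: age is recorded as "Patient's Age: _____ years", and height, weight and BMI are also open fields without bands.

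**The concern.** A continuous variable can be stratified only by cutting it into categories. Two consequences follow, and both remain even if each modifier is judged by a correct group-by-stratum interaction test.

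- **Lost information.** Patients within a band are treated as identical although their exact values are on the proforma. With 60 patients there is little power for interactions to begin with.
- **Free choice of cut.** With no cut written down, the plan allows it to be set once the USSQ totals are known by group. The plan describes no blinding, and one arm receives a capsule and the other a tablet. A cut picked because it shows a difference does not have a 5% error rate.

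At stake is the reliability of any statement that the drug difference depends on age or body size. Two analysts could both follow this plan and report different modifiers.

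**Working it through.** **Inputs.** The Sample size paragraph gives USSQ scores of "76 \pm 8 in tamsulosin group and 61 \pm 8.8 in solefinacin group", 90% power, 95% confidence, 7 per group calculated and 30 per group planned. Alpha is 0.05, taken as two-sided. The distribution of the four variables is not given, so normal and uniform shapes are assumed in turn.

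**The plan's own figure.** Pooled SD = √((8² + 8.8²)/2) = 8.41. n per group = (8² + 8.8²)(1.960 + 1.282)²/15² = 6.61, rounded up to 7, or 14 in total. This reproduces. With 30 per group, power for the 15-point main effect exceeds 99.9%.

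**Information kept after cutting (linear effect).** For a two-way split of a normal variable with a proportion p below the cut c, the share kept is φ(c)²/(p(1−p)). For a uniform variable it is 3p(1−p), or 1 − 1/k² for k equal groups.

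| Cut | Kept | Lost |
|---|---|---|
| Normal, median | 2/π = 0.637 | 36% |
| Normal, 70th percentile | 0.576 | 42% |
| Normal, 80th percentile | 0.490 | 51% |
| Normal, 90th percentile | 0.342 | 66% |
| Normal, 3 / 4 / 5 equal groups | 0.793 / 0.861 / 0.897 | 21% / 14% / 10% |
| Uniform, median | 0.750 | 25% |
| Uniform, 3 equal groups | 0.889 | 11% |

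The uniform rows matter for age, which eligibility limits to 20 to 50 years.

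**Interaction power, 30 per arm, SD 8.41, normal variable.** Kept continuous, the standard error of the interaction slope is about 8.41 × √(2/30) = 2.17 points per SD. With a median split there are 15 patients per cell, so the standard error of the interaction contrast is 8.41 × √(4/15) = 4.34. The two halves lie 1.596 SD apart on average, which gives 4.34/1.596 = 2.72 per SD. The ratio (2.17/2.72)² = 0.637 agrees with the table. The normal approximation at 4 points per SD gives Φ(4/2.17 − 1.96) = 45% against Φ(4/2.72 − 1.96) = 31%. Simulation uses the t distribution and random covariate values, and comes out slightly lower:

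| True interaction (points per SD) | Continuous | Median split |
|---|---|---|
| 2 | about 14% | about 11% |
| 4 | about 42% | about 28% |
| 6 | about 74% | about 53% |

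**False-modifier rate per variable.** Simulation with no true interaction, 30 per arm, interaction test at 0.05, 5,000 runs per setting:

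| Method | Rate |
|---|---|
| Continuous term | 4.4–5.0% |
| Median cut fixed in advance | 4.5–5.1% |
| Best of three cuts (tertiles, median) | about 11% |
| Best cut, 20th to 80th percentile | about 28% |

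Narrowing the exhaustive search to the central 50% gives 24%; widening it to the central 80% gives 36%.

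**What is left after repair.** Four independent tests at 0.05 give 1 − 0.95⁴ = 18.5% for at least one false positive. Keeping the variables continuous does not remove this.

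**The case against.** Several points on the other side are sound.

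- A reader might infer that about a third of the information is always lost. The documents do not support this. It requires two groups, a median cut, a roughly normal variable and a linear effect, and the plan fixes none of these.
- A reader might infer that cuts will be chosen after the results are seen and that a 28% error rate is to be expected. The plan is silent on when cuts are set. It permits a late choice but does not announce one, and 28% describes an analyst who tries every cut in the range and keeps the best.
- Categorisation is itself inferred from the word stratification. That is its ordinary meaning, and no other method is described.
- A modifier of 6 points per SD is very large: it would move the 15-point difference from 9 to 21 points across ±1 SD. At 2 points per SD both methods have little power, so continuous modelling does not make this analysis strong.
- The plan could fix its cuts in advance and call the analyses exploratory. That would remove the inflation from cut choice, but not the lost information.
- BMI is derived from height and weight, so the four are not separate modifiers, and multiplicity remains.

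These points limit the size and reach of the concern. They do not remove it: no cut is specified, exact values are collected, and a method that uses them costs almost nothing. Errors from reading within-stratum p-values without an interaction test are a different issue and are not counted here.

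**Conclusion.** The concern holds in a conditional form. The plan stratifies four variables that it also calls quantitative, without cut-points. The information lost depends on the cuts: 36% for a median split of a normal variable, about 25% for a uniform one, 10–21% with 3 to 5 equal groups of a normal variable, and 42–66% for two-way cuts at the 70th to 90th percentile. A data-chosen cut can raise the false-modifier rate per variable from 5% to about 11% with a mild search, and to about 28% with an exhaustive search from the 20th to the 80th percentile.

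The power figures assume a normal variable, a straight-line interaction, 30 analysed patients per arm and SD 8.41. A reader might also infer that the trial's main result is compromised. It is not: the overall comparison of total USSQ score does not use these strata. The consequence is confined to the secondary modifier analysis. The change is worth making because it is cheap and needs no new data.

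**What to change.** In DATA ANALYSIS PROCEDURE, take age, height, weight and BMI out of the stratification list. For each, specify a linear model of total USSQ score on group, the variable kept continuous, and group × variable. Report the change in treatment difference per stated unit (for example per 10 years of age or per 5 kg/m² of BMI) with a 95% CI.

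If bands are wanted for display, write the cut-points into the plan before any USSQ total is seen and attach no p-values to them. Label these analyses exploratory, since four tests at 0.05 can still give up to about 18.5% false positives, and note that BMI is derived from height and weight.

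The cost is a few sentences. The models run in the planned SPSS on data already on the proforma. The downside is an assumed straight-line relation, which a plot of USSQ score against each variable by group can check.

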10. Mirani K K, Ather M H (August 08, 2022) Translation and Validation of the Ureteral Stent Symptoms Questionnaire in Urdu. *Cureus* 14(8): e27764. DOI 10.7759/cureus.27764

ANNEXURE-I PROFORMA

GROUP: _____

Serial No: _____

Case No: _____

Patient's Name: _____

Patient's contact #: _____

S/O, D/O, W/O: _____

Patient's Age: _____ years

Gender: Male Female

Height: _____

Weight: _____

BMI: _____

Any Addiction: Yes No _____

Diabetes: Yes No

Hypertension: Yes No

Smoker: Yes No

Occupation: _____

Surgical Procedure: _____

Indication of stent placement: _____

Date of stent placement: _____

Length of stent placed: _____ (cm)

Total USSQ score: _____

ANNEXURE-II USSQ(Stent in situ)

We are interested to know about various aspects of your health, following insertion of the stent and the effect the stent has had on your health.

**Please complete the following questionnaire, which has different sections.
Please answer all questions in each section.**

(We would be grateful if you could complete and post the questionnaire within seven days)

Please complete:

Today's Date: / /

Date of Birth: / /

You will see that some questions ask if you have a symptom occasionally, sometimes or most of the time.

Occasionally	=	less than one third of the time
Sometimes	=	between one and two thirds of the time
Most of the time	=	more than two thirds of the time

URINARY SYMPTOMS

Please answer the questions thinking about the urinary symptoms you have experienced following insertion of the stent.

Please put a tick in one box for each question

Please think about your experience since insertion of the stent.

U1. During the day, how often do you pass urine, on average?

Less than hourly	 5	Every 3 hourly	 2
Hourly	 4	Every 4 hours or more	 1
Every 2 hourly	 3		

U2. During the night, how many times do you have to get up to pass urine, on average?

None	 1	3	 4
1	 2	4 or more	 5
2	 3		

U3. Do you have to rush to the toilet to urinate?

Never	 1	Most of the time	 4
(more than two thirds of the time)			
Occasionally	 2	All of the time	 5
(less than one third of the time)			
Sometimes	 3		
(between one and two thirds of the time)			

U4. Does urine leak before you can get to the toilet?

Never	 1	Most of the time	 4
Occasionally	 2	All of the time	 5
Sometimes	 3		

U5. Do you leak urine without feeling the need to go to the toilet?

Never	 1	Most of the time	 4
Occasionally	 2	All of the time	 5
Sometimes	 3		

U6. how often do you feel that your bladder has not emptied properly after you have passed urine?

Never  1	Most of the time  4 (more than two thirds for the time)
Occasionally  2 (less than one third of the time)	All of the time  5
Sometimes  3 (between one and two thirds of the time)	

U7. Do you have a burning feeling when you pass urine?

Never  1	Most of the time  4
Occasionally  2	All of the time  5
Sometimes  3	

U8. How often do you see blood in your urine?

Never  1	Most of the time  4
Occasionally  2	All of the time  5
Sometimes  3	

U9. How much blood do you see in your urine?

Do not see any blood  1	Urine is heavily blood stained  3
Urine is slightly blood stained  2	Urine is heavily blood stained and has clot(s)  4

U10. Overall, how much of a problem are your urinary symptoms to you?

Not at all  1	Quite a bit  4
A little bit  2	Extreme  5
Moderate  3	

U11. If you were to spend the rest of your life with the urinary symptoms, if any, associated with the stent just the way they are, how would you feel about it?

Delighted  1	Mostly dissatisfied  5
Pleased  2	Unhappy  6
Mostly satisfied  3	Terrible  7
Mixed feelings (about equally satisfied and dissatisfied)  4	

Please go to next section --

BODY PAIN (for women):

This section asks about the **body pain or discomfort**, which you associate with the stent.

Please think about your experience **following insertion of the stent**.

P1. Do you experience body pain or discomfort in association with the stent?

[figure not shown]
YES ₁, please go to question P2

NO ₂, please go to next section on General Health

[figure not shown]
(Ignore questions P2 to P9)

P2. Think of the drawings below as the drawings of your body. Please **mark (X) or shade the site(s) where you experience pain or discomfort in association with the stent typically (e.g. during the day to day activities, whenever you pass urine)**

If you get pain at more than one site, please use a **separate mark for each site**.

Front View

[figure not shown]
Back View

The numbers I - IV represent following areas for the right and left sides

I – Kidney front/side area III – Bladder area II - Groin area IV – Kidney back (loin) area

Please use O for any other marked area and write the name of the site

P3. Please place a **mark (X)** to a point on the line below that indicates your pain or discomfort in association with the stent. **Please put a separate mark for each site** if the pain or discomfort is different in severity and write the corresponding number of each site used in the drawing above.

No Pain or discomfort

Worst Possible Pain

BODY PAIN (for men):

This section asks about the **body pain or discomfort, which you associate with the stent.**

Please think about your experience **following insertion of the stent.**

[figure not shown]
[figure not shown]
P1. Do you experience body pain or discomfort in association with the stent?

YES **1, please go to question P2**

NO **2, please go to next section on General Health** (Ignore questions P2 to P9)

P2. Thinking the drawings below as the drawings of your body, **mark (X) or shade the site(s) where you experience pain or discomfort in association with the stent typically (e.g. during the day to day activities, whenever you pass urine)**

If you get pain at more than one site, please use a **separate mark for each site.**

The numbers I - V represent following areas for the right and left side.

I – Kidney front/side area

IV – Kidney back (loin) area

II - Groin area

V – Penis

III – Bladder area

Please use **O** for any other marked site and name that site.

P3. Please place a **mark (X)** to a point on the line below that indicates your pain or discomfort in association with the stent. **Please put a separate mark for each site** if the pain or discomfort is different in severity and write the corresponding number of each site used in the drawing above.

No Pain or discomfort

Worst Possible Pain

P4. Which of the following statements best describe your experience regarding physical activities and the pain or discomfort in association with the stent?

I do not experience any pain or discomfort during physical activities 1

I experience pain or discomfort only when I perform **vigorous activities** 2
(e.g. strenuous sports, lifting heavy objects)

I experience pain when I perform **activities of moderate severity** but not with basic activities 3
(e.g. walking few hundred yards, driving a car)

I experience pain even when I perform **basic activities** of daily living 4
(e.g. walking indoors, dressing)

I experience pain while also **being at rest** 5

P5. Does the pain or discomfort, in association with the stent, interrupt your sleep?

Never 1 Most of the time 4

Occasionally , All of the time 5

Sometimes 3

P6. Do you experience pain or discomfort, in association with the stent, while passing urine?

Never 1 Most of the time 4

Occasionally 2 All of the time 5

Sometimes 3

P7. Do you experience pain or discomfort in the kidney area, while passing urine?

No 1

Yes ,

P8. How frequently have you required painkillers to control the pain or discomfort associated with the stent?

Never 1 Most of the time 4

Occasionally 2 All of the time 5

Sometimes 3

P9. Overall, how much does the pain or discomfort, in association with the stent, (as distinct from other symptoms) interfere with your life?

Never 1 Most of the time 4

Occasionally , All of the time 5

Sometimes 3

Please go to next section --

GENERAL HEALTH:

Following insertion of the stent:

G1. Have you had difficulty in performing light physical activities (e.g. walking short distances, driving a car)?

Usually with no difficulty  1	Usually did not do because of the stent  4
Usually with some difficulty  2	All of the time  0
Usually with much difficulty  3	

G2. Have you had difficulty in performing heavy physical activities (e.g. strenuous sports, lifting heavy objects)?

Usually with no difficulty  1	Usually did not do because of the stent  4
Usually with some difficulty  2	All of the time  0
Usually with much difficulty  3	

G3. Have you felt tired and worn out?

Never  1	Most of the time (more than two thirds of the time)  4
Occasionally (less than one third of the time)  2	All of the time  5
Sometimes (between one and two thirds of the time)  3	

G4. Have you felt calm and peaceful?

All of the time  1	Occasionally (more than two thirds of the time)  4
Most of the time (less than one third of the time)  2	Never  5
Sometimes (between one and two thirds of the time)  3	

G5. Have you enjoyed your social life (going out, meeting friends and so on)?

All of the time  1	Occasionally  4
Most of the time  2	Never  5
Sometimes  3	

G6. Have you needed extra help from your family members or friends?

Never  1	Most of the time  4
Occasionally  2	All of the time  5
Sometimes  3	

Please go to next section –

WORK PERFORMANCE:

W1. Regarding your employment status, are you

In full time employment 1

Student 4

In part time employment 2

Unemployed, looking for work 5

Retired on health ground 3

Retired for other reason (including age) 6

Not working for other reason (please specify) 7

W2. Following insertion of the stent, how many days did the symptoms associated with the stent keep you in bed all or most of the day?

Day(s)

W3. Following insertion of the stent, for how many half days or more did you cut down your routine activities because of the symptoms associated with the stent?

Half Day(s)

**Please answer the questions below (W4 –W7) only if you are in active paid work.
(Otherwise ignore questions W4 – W7).**

W4. a) Job title or description of your role: _____

b) Are you an: Employee 1 Employer 2 Self employed 3

Please answer following questions if you have worked after insertion of the stent,

W5. Have you worked for short periods of time or taken frequent rests because of the symptoms associated with the stent?

Never 1 Most of the time 4

Occasionally 2 All of the time 5

Sometimes 3

W6. Have you worked at your usual job, but with some changes because of the symptoms associated with the stent?

Never 1 Most of the time 4

Occasionally 2 All of the time 5

Sometimes 3

W7. Have you worked your regular number of hours?

Never 1 Most of the time 4

Occasionally 2 All of the time 5

Sometimes 3

Please go to next section –8

SEXUAL MATTERS:

Please tick one box for each question by thinking about your experience following insertion of the stent.

S1. Currently, do you have an active sex life?

No 1, Please answer question S2 and go to next section (Ignore questions S3 and S4).

Yes 2, Please go to question S3 (Ignore question S2).

S2. (i) If NO sex life, how long ago did this stop?

After insertion of the stent 1

Before insertion of the stent 0

(ii) AND, why did this stop?

Because of the problems associated with the stent 10

Did not attempt any sexual activity 0

Some other reason – not to do with the symptoms of the stent 0

(Ignore questions S3 – S4)

Please answer questions S3 and S4, only if you have answered 'yes' to question S1.

Please think about your experience following insertion of the stent.

S3. Do you have pain when you have sexual intercourse?

Not at all 1 Severe 4

Mild 2 Extreme 5

Moderate 3

S4. How satisfied are you with your sex life?

Very satisfied 1 Dissatisfied 4

Satisfied 2 Very dissatisfied 5

Not sure 3

Please go to next section ---

ADDITIONAL PROBLEMS:

The following questions ask about your experience following insertion of the stent. Please indicate your experience by ticking the appropriate box.

A1. How many times have you felt you may be suffering from a urinary tract infection (e.g. running temperature, feeling unwell and pain while passing urine)?

Never 1

Most of the time 4

Occasionally 2

All of the time 5

Sometimes 3

A2. Have you needed to take antibiotics as a result of insertion of the stent? (Please ignore the course of antibiotics, which may have been given at the time of insertion of the stent.)

Not at all 1

Two Courses 3

One Course 2

Three or more Courses 4

A3. Have you needed to seek help of a health professional (such as GP, nurse) due to any problem associated with the stent?

Never 1

Twice 3

Once 2

Three or more times 4

A4. Have you needed to visit the hospital due to any problem associated with the stent?

Never 1

Twice 3

Once 2

Three or more times 4

GQ In the future, if you were advised to have another stent inserted, how would you feel about it?

Delighted 1

Mostly dissatisfied 5

Pleased 2

Unhappy 6

Mostly satisfied 3

Terrible 7

Mixed feelings (about equally satisfied and dissatisfied) 4

AQ. If there are any comments you would like to make about the questionnaire or any of your symptoms, please use the space below.

THANK YOU VERY MUCH FOR YOUR HELP

All information will remain confidential

10
